***Patient enrollment:***

A maximum of 26 patients meeting the inclusion criteria and not meeting the exclusion criteria will be enrolled in the study. The enrollment period is expected to last for at least 12 months.

***Data collection and analysis:***

The final data will be pooled and analyzed by the investigators.

**E. Statistical methods**

Continuous variables will be compared between the groups using repeated measures analysis of variance (ANOVA). Significant interactions will be followed by time trend analyses stratified by intervention group. For all pair-wise testing, we will adjust for multiple comparisons using Tukey's method. Statistical significance will be declared at  $p < 0.05$ .

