## **D. Research Design and Methods**

### ***Specific Aim 1:***

To examine the effect of short-term LLTS on echocardiographic markers of diastolic dysfunction in patients with diastolic dysfunction. This is a prospective, randomized, 2x2 cross over pilot study. Patients who have been diagnosed with diastolic dysfunction by echocardiogram within 36 months of study enrollment will be eligible for enrollment in the study. Patients will be excluded if they have any of the following: left ventricular dysfunction (left ventricular ejection fraction <40%), significant valvular disorder (i.e., prosthetic valve or hemodynamically significant valvular diseases), recent (<6 months) stroke or myocardial infarction, severe heart failure (class III or IV), recurrent vasovagal syncope, unilateral or bilateral vagotomy, pregnancy or nursing and sick sinus syndrome (without a pacemaker), 2nd or 3rd degree AV block, bifascicular block or prolonged (PR>300ms) 1st degree AV block. Patients will be recruited from the outpatient clinics of OUHSC. All patients will receive 2 separate, 1-hour sessions, at least 1 day apart, of active and sham LLTS, with the sequence of the sessions being randomized. Patients will be randomly assigned (1:1) to active/sham or sham/active LLTS. LLTS will be performed using a transcutaneous electrical nerve stimulation (TENS) device with electrodes attached to the tragus of the ear, which is innervated by auricular branch of the VN. The SaluSTIM Digital TENS Unit distributed within the US by US Medical Inc will be used for LLTS or sham stimulation. The device will be connected to a clip electrode that will be attached to the external ear. In the active group, the ear clip electrode will be attached to tragus in the active stimulation group (Figure 3). This device was deemed as non-significant risk by the FDA (see attached letter). The same TENS protocol will be followed in sham LLTS arm, but the electrode will be placed on the ear lobe, which is devoid of vagus innervation. The TENS unit will be set at a pulse width of 100  $\mu$ s and a pulse frequency of 20 Hz. Amplitude will be titrated to the level of sensory threshold, typically in the range of 10–50 mA. In patients with pacemakers, the pacemaker will be tested with the TENS unit to assess for interaction. In case of interaction (the stimulation artifact of the TENS unit picked up by the pacemaker), the patients will be excluded from the study. Echocardiography will be performed after 30 minutes of LLTS or sham stimulation to assess diastolic function (Acuson SC2000, Siemens). Two-dimensional long axis and short axis LV images will be obtained and Pulse-wave Doppler spectra of mitral inflow (E and A waves), as well as mitral annulus tissue Doppler spectra will be recorded. The early diastolic mitral annulus velocity ( $e'$ ) will be used to assess diastolic function as previously described. The ratio of early to late mitral inflow Doppler velocity (E/A ratio) is a marker of LV diastolic relaxation and stiffness, and the E/ $e'$  ratio correlates well with LV filling pressures. In addition, LV diastolic strain, a sensitive marker of diastolic LV function, which independently predicts outcomes in patients with HFpEF, will be obtained off-line using a speckle-tracking algorithm (Acuson SC2000 eSie VVITM).

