
### ***Specific Aim 2:***

To examine the effect of short-term LLTS on heart rate variability in patients with diastolic dysfunction. For this Aim, the same group assignment as in Aim 1 will be used. HRV is a marker

of vagus nerve activity and can be easily measured by software calculating the distance between consecutive R waves on the ECG. Importantly, measures of HRV have been inversely correlated with inflammatory cytokines (C-reactive protein, IL-6) in the general population. At each visit, serial 5-minute ECGs will be obtained for HRV analysis every 15 minutes of stimulation (total of 4 recordings). ECG will be obtained in the supine position after resting for 15 minutes. This test will be done using a PC-Based ECG device. Analysis and interpretation of the HRV data will be performed in a blinded fashion.

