***Sample size and power calculations:***

For purposes of sample size calculations we have simplified the analysis to focus on the difference in the E/e' ratio between the 2 intervention groups. Assuming a mean  $\pm$  standard deviation E/e' ratio  $15.2 \pm 6.4$  and 40% reduction in the LLTS group, 26 patients would provide greater than 80% power to detect the specified effect sizes at a two-sided  $\alpha$  level of 0.05.

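### Section E describes a between-group repeated measures ANOVA for a 2x2 crossover: as worded, the HRV treatment effect can lose its pairing, and no period term is given for any outcome

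*Combined protocol and SAP*

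**What the plan says.** Section D, Specific Aim 1, sets up a 2x2 crossover: "All patients will receive 2 separate, 1-hour sessions, at least 1 day apart, of active and sham LLTS". What is randomised is the order: "Patients will be randomly assigned (1:1) to active/sham or sham/active LLTS". Echo is taken once in each session ("Echocardiography will be performed after 30 minutes of LLTS or sham stimulation to assess diastolic function"). HRV, under Specific Aim 2, is taken four times in each: "serial 5-minute ECGs will be obtained for HRV analysis every 15 minutes of stimulation (total of 4 recordings").

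Section E is the whole analysis plan. For all continuous outcomes it says "Continuous variables will be compared between the groups using repeated measures analysis of variance (ANOVA"), and then "Significant interactions will be followed by time trend analyses stratified by intervention group". It adds Tukey adjustment for pairwise tests and a 0.05 significance level. It names no patient factor, within-patient contrast, period or sequence, and no other section supplies them. The sample size section also works with the E/e' "ratio between the 2 intervention groups".

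**The concern.** In a 2x2 crossover the treatment effect is estimated inside each patient, as active minus sham, with allowance for a shift between first and second session. Section E instead reads like the plan for a parallel-group trial: an intervention factor between subjects, time as the repeated factor, and an interaction followed up by time trends in each group.

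The consequence differs by outcome.

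- **HRV.** Four recordings per session are enough to satisfy the term repeated measures without ever linking a patient's two sessions. If the plan is followed that way, between-patient variation stays in the error term for the treatment main effect. The test becomes very conservative, the intervals are wider than the design allows, and a real effect in Specific Aim 2 could be missed.
- **Echo.** With one measurement per session, the only possible repeat is the session itself, so pairing is implied. Only the period term is missing.

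**Working it through.** **1. The plan's own power figure.** Inputs from the sample size section: mean 15.2, SD 6.4, 40% reduction, 26 patients, two-sided 0.05. The effect is 0.40 × 15.2 = 6.08 units, or 6.08/6.4 = 0.95 SD.

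- 26 measurements in each condition, pairing ignored: power 92.9% (normal) or 91.9% (t).
- Paired t: 90.8%, 97.6% and 99.6% at assumed within-patient correlation (rho) 0, 0.3 and 0.5.
- 13 versus 13 as separate groups: 67.8% (normal) or 64.2% (t).

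So the claim of more than 80% holds when each patient contributes both conditions. Adding a period term (24 df) leaves it at 90.7%, 97.5% and 99.6%.

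**2. HRV treatment main effect.** The documents give no HRV variance, correlation or effect size, so these inputs are assumptions. Single-recording variance is 1, of which 0.3 is residual; the other 0.7 is split between patient (P) and patient-by-session (S). There are 26 patients (13:13) and four recordings per session.

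- Variance of a session mean: P + S + 0.3/4 = 0.775 throughout.
- Correlation of a patient's two session means: P/0.775.
- Between-group standard error (50 df): √(2 × 0.775/26) = 0.244.
- Within-patient standard error (24 df): √(2 × (S + 0.075)/26).

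| P / S | Correlation | Within-patient SE | SE ratio, between/within |
|---|---|---|---|
| 0.3 / 0.4 | 0.39 | 0.191 | 1.28 |
| 0.4 / 0.3 | 0.52 | 0.170 | 1.44 |
| 0.5 / 0.2 | 0.65 | 0.145 | 1.68 |
| 0.6 / 0.1 | 0.77 | 0.116 | 2.10 |

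Simulation, 40,000 replicates per row, between-group v within-patient (the within-patient test includes period):

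| Correlation | Null rejection | Power at 0.4 SD | Mean 95% CI half-width (SD) |
|---|---|---|---|
| 0.39 | 1.4% v 5% | 33% v 52% | 0.49 v 0.39 |
| 0.52 | 0.6% v 5% | 31% v 62% | 0.49 v 0.35 |
| 0.65 | 0.2% v 5% | 29% v 75% | 0.49 v 0.30 |
| 0.77 | 0.01% v 5% | 25% v 91% | 0.49 v 0.24 |

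**3. HRV treatment-by-time.** With an assumed effect rising 0, 0.15, 0.30, 0.45 SD over the four recordings, power is about 42% between-group and 41% within-patient. Patient and session effects that are constant over a session cancel, so there is no real loss.

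**4. HRV with patient as the only block and one pooled residual.** This is another possible fit of the same sentence. Null rejection is 30%, 27%, 23% and 16% for the four rows above, because recordings from one session are treated as independent given the patient.

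**5. Echo, period term omitted v included.** Plan's SD 6.4; assumed effect of 20% (0.20 × 15.2 = 3.04 units); 13:13; 100,000 replicates.

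| rho | Power, 3-unit shift | CI half-width, 3-unit shift | Power, 1.5-unit shift |
|---|---|---|---|
| 0.3 | 44% v 50% | 3.3 v 3.0 | 49% v 50% |
| 0.5 | 56% v 64% | 2.8 v 2.6 | 62% v 64% |
| 0.7 | 76% v 85% | 2.3 v 2.0 | 83% v 85% |

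With no shift nothing is lost. At the plan's 40% effect and a 3-unit shift, power is 96% v 98%, 99% v more than 99%, and more than 99% for both.

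Bias from omitting period is shift × (difference in sequence sizes)/26. For a 3-unit shift it is 0 at 13:13, 3 × 2/26 = 0.23 units at 14:12, and 3 × 4/26 = 0.46 at 15:11. Type I error stayed below 5% in these settings. A more uneven 16:10 split, with a 0.5 SD shift and rho 0.7, gave 5.9%.

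**The case against.** The strongest reply is that this is a gap in specification and not a wrong analysis. Section E does name repeated measures ANOVA, Aim 1 makes clear that each patient has both sessions, and nothing instructs anyone to treat 26 patients as 52. Aim 2 also says "For this Aim, the same group assignment as in Aim 1 will be used", and the only random assignment in Aim 1 is to sequence. If *group* means sequence, the group-by-session interaction is the period-adjusted treatment test and nothing is lost. Time trends by intervention could equally be trends within active and within sham sessions. Finally, every HRV figure rests on assumed inputs, and the one test Section E explicitly follows up, the interaction, is hardly affected.

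Much of this stands. The wording permits the unpaired HRV analysis and does not compel it; the sequence reading is open; the HRV magnitudes are illustrative. But Section E writes of intervention groups, and the sample size section of two intervention groups and an LLTS group, so the more natural meaning of *group* is active versus sham. The direction of the loss does not depend on the chosen inputs: with any positive within-patient correlation rho between session means, ignoring pairing overstates the standard error by 1/√(1 − rho). That different fits of the same sentence give null rejection from near 0% to 30% is itself a reason to fix the error term before the data are seen.

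**Conclusion.** The concern holds and should be fixed. Section E does not describe the analysis of a 2x2 crossover. Read as worded, with intervention as the group and time as the repeat, it costs the HRV treatment main effect about 19 points of power (52 − 33) at a correlation of 0.39 and about 66 points (91 − 25) at 0.77, for an assumed 0.4 SD effect. The error is towards missed effects, not false positives, unless the pooled-residual fit is used. The HRV interaction test is essentially unaffected.

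For echo the matter is minor. At 13:13, omitting period costs precision only if there is a period shift; bias needs unequal sequences as well. The E/e' power claim is not undermined.

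Confidence is high that the specification is missing and in the direction of the loss. Its size for HRV depends on variance shares and an effect size that the documents do not give.

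**What to change.** Rewrite the first part of Section E along these lines:

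- For every continuous outcome, compare active with sham within patient, with treatment and period as within-patient factors and patient as the blocking (random) factor. Report the difference with a 95% CI.
- For HRV, add recording time, treatment-by-time and a patient-by-session error term, and test treatment within patient. The patient-by-session term is needed to avoid the inflated null rejection shown for the pooled residual.
- Replace *group* with *treatment* or *sequence*, whichever is meant.

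The named repeated measures ANOVA can be kept; a linear mixed model is one acceptable way to fit it. The planned time trends can stay, and the choice of main HRV contrast remains with the sponsor. The cost is a short wording change and one degree of freedom for period, with no new data, visits or patients.

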#### **A. Specific aims:**

##### ***Specific Aim 1:***

To examine the effect of short-term LLTS on echocardiographic markers of diastolic dysfunction in patients with diastolic dysfunction.

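### No primary endpoint is named and continuous measures are tested at p<0.05; across four echo measures the false-positive chance is 18.5% if independent, 9.4% at an assumed correlation of 0.9

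*Combined protocol and SAP*

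**What the plan says.** The analysis plan is the short paragraph that opens Section E (Statistical methods). It states: "Continuous variables will be compared between the groups using repeated measures analysis of variance (ANOVA"). The one multiplicity provision is: "For all pair-wise testing, we will adjust for multiple comparisons using Tukey's method". The threshold follows: "Statistical significance will be declared at" p<0.05. Neither this section nor any other calls an outcome primary or secondary, or ranks the outcomes.

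Aim 1 is plural: "To examine the effect of short-term LLTS on echocardiographic markers of diastolic dysfunction in patients with diastolic dysfunction". Section D, under Specific Aim 1, says "This is a prospective, randomized, 2x2 cross over pilot study" and then names four measures:

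- e', which is given the role of assessing diastolic function;
- E/A: "The ratio of early to late mitral inflow Doppler velocity (E/A ratio) is a marker of LV diastolic relaxation and stiffness";
- E/e', described by its relation to filling pressure;
- strain: "In addition, LV diastolic strain, a sensitive marker of diastolic LV function".

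Aim 2 adds heart rate variability (HRV), recorded at each visit "every 15 minutes of stimulation (total of 4 recordings"). The HRV indices are not listed.

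The sample size paragraph in Section E uses E/e' alone: mean 15.2, SD 6.4, a 40% reduction, 26 patients, power above 80% at two-sided 0.05. It presents the focus on E/e' as a simplification made for sizing, not as the choice of a deciding endpoint.

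**The concern.** The power claim covers one test of one measure at 0.05, but the analysis paragraph applies the same threshold to continuous variables without distinction. No rule says which result answers Aim 1, or how a mixed result is to be read, for example if strain is significant and E/e' is not. The text would let a reader defend E/e' (used for sizing), e' (given the assessment role) or strain (called sensitive) as the main measure after seeing the results.

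Two features raise the stakes. Section G says these proof-of-concept investigations will supply the first evidence of the effect in humans and may form the basis for later studies, so a chance finding on one measure could steer the next trial. The data are also to be analysed by the investigators, and the plan states blinded analysis only for HRV. Fixing the endpoint in advance is therefore an important safeguard for the echo results.

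**Working it through.** **1. The plan's own figure.** Inputs from the sample size paragraph: mean 15.2, SD 6.4, 40% reduction, n = 26, two-sided 0.05.

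- Difference: 0.40 × 15.2 = 6.08.
- If 6.4 is the SD of a single measurement and ρ is the within-patient correlation (not given, so assumed), the SD of the active-sham difference is 6.4 × √(2(1 − ρ)). That is 9.05 at ρ = 0 and 6.40 at ρ = 0.5.
- Noncentrality: 6.08 / (9.05/√26) = 3.43, or 6.08 / (6.40/√26) = 4.84.
- With a 2×2 crossover t test on 24 df, power is 90.7% or 99.6%.

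The statement of more than 80% power is reproduced, for a single test of E/e'.

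**2. Does Tukey's method help?** It adjusts comparisons among means of one variable. Each echo measure has one active-sham contrast. For two means on 24 df the Tukey critical value is q(0.95; 2, 24)/√2 = 2.064, which equals the unadjusted t(0.975; 24) = 2.064. It changes nothing for a single contrast and does not act across different variables. It does have a use among the four HRV recordings in a session.

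**3. Independent measures.** The chance of at least one false positive in k tests at 0.05 is 1 − 0.95^k.

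- k = 4: 1 − 0.8145 = 0.1855.
- k = 3: 1 − 0.8574 = 0.1426.

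**4. Correlated measures.** The echo measures are related, so take test statistics that are normal with a common correlation r. With c = 1.96, φ the normal density and Φ its distribution function:

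P = 1 − ∫ φ(x) [Φ((c − √r·x)/√(1−r)) − Φ((−c − √r·x)/√(1−r))]^k dx

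The check column simulates a 26-patient crossover (13 per sequence, t on 24 df, 200,000 trials).

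| r (assumed) | four measures | simulation, four | three measures |
|---|---|---|---|
| 0 | 18.5% | 18.5% | 14.3% |
| 0.5 | 15.6% | 15.8% | 12.5% |
| 0.9 | 9.4% | 9.5% | 8.4% |
| 0.95 | 8.0% | 8.0% | – |
| 0.99 | 6.3% | 6.4% | – |

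The comparison is 5% for one named endpoint. HRV is left out because its indices are not listed.

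**5. What relying on E/e' alone would mean.** Same model as step 1, with smaller true effects:

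| True reduction | Difference | Power, ρ = 0 | Power, ρ = 0.5 |
|---|---|---|---|
| 40% | 6.08 | 91% | 99.6% |
| 20% | 3.04 | 38% | 64% |
| 15% | 2.28 | 23% | 42% |

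Power of 80% needs a reduction of 34.1% (5.18) at ρ = 0 or 24.1% (3.67) at ρ = 0.5.

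**The case against.** The best defence is that this is a pilot, described throughout as proof of concept. Aim 1 is to examine effects on markers, and no passage says that one significant marker makes the study a success. On that view the chance of at least one false positive describes a decision rule that the plan does not contain. The independent case is also the least plausible: E/e' contains e', and E/A shares E with E/e', so three of the four measures are linked by construction. The count of four is inferred. Finally, the text gives e' and strain some claim to be the main measure, so preferring E/e' is partly a judgement.

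Much of this stands as a matter of weight. Strict error control over every outcome is not required here, 18.5% is the upper end of the range, and a well-argued choice of another primary measure would also close the gap. It does not remove the point. The plan declares significance and claims power at a stated alpha, so it is not purely descriptive. The absence of a success rule is the defect itself, because the rule can then be settled after the results are known. The error rate also stays above 5% at every correlation examined and when only three measures are counted.

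**Conclusion.** The point holds. Followed as written, Section E tests several echo measures at the same threshold with no deciding endpoint and no adjustment that acts across them. For four measures the false-positive chance runs from 18.5% (independent) through 9.4% (correlation 0.9) to 6.3% (correlation 0.99).

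These figures assume no true effect on any measure, one common correlation, a two-sided test of each measure, and that the four measures named in Section D are the ones tested. The size is therefore uncertain, but the direction is not. Because this is a pilot, it is a change that should be made rather than a flaw that invalidates the study.

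**What to change.** Add to the analysis paragraph of Section E wording such as:

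> The primary endpoint for Aim 1 is the active-sham difference in E/e', tested at two-sided 0.05. The measures e', E/A and diastolic strain, and all HRV measures, are secondary or exploratory and will be reported with 95% confidence intervals; none of them alone makes Aim 1 positive. Tukey's method applies to comparisons among HRV recording times.

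E/e' is the natural choice because the trial is already sized on it. If the sponsor prefers another measure, it should give the reason and redo the sample size for that measure. A formal testing order for the secondary measures is optional.

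The cost is two or three sentences and no extra patients. The downside is that no confirmatory claim could be made on the other echo measures if E/e' misses. That could happen: the 40% reduction is attributed to reference 31, which Section C describes as an atrial fibrillation study and for which it reports no E/e' result. Low power at a smaller effect is a reason to interpret a miss carefully and to show the intervals. It is not a reason to leave the deciding measure open.

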**2. Risks and assess likelihood and seriousness:**

Transcutaneous VNS has generally been shown to be safe and well tolerated with only minor side effects, like tingling sensation, dysesthesia, skin redness and pressure marks at the site of stimulation, painful stimulation, dizziness, mild dyspnea and headaches. No significant effects on heart rate, blood pressure, or peripheral microcirculation could be detected during short term tVNS in a sample of 10 patients with tinnitus and in 22 healthy volunteers. In a pilot study of 24 patients with tinnitus treated with tVNS over 3-10 weeks, 2 adverse cardiac events (one classified as a severe adverse event) were registered but considered very unlikely to have been caused by tVNS since other explanations for the symptoms were evident. One patient had experienced sinus arrhythmic episodes already in the past, and in the other patient comorbid hypertension had caused concentric cardiac hypertrophy which might have contributed to the described temporary left bundle branch block. Retrospective analyses of ECG parameters revealed a trend toward shortening of the QRS complex by tVNS. This was observed after the 2 patients with cardiac adverse events were excluded from the analysis, but not when the whole sample of patients was analyzed. There was definitely no prolongation of the QRS complex which is a known predictor of cardiac morbidity and mortality. In conclusion, in subjects with no known pre-existing cardiac pathology, there has been no indication of arrhythmogenic effects of tVNS. This is in line with the low incidence of adverse cardiac reactions during the long-term experience in more than 50,000 patients with implanted left VNS for treatment of epilepsy and depression.

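### Repeated measures ANOVA with no rule for incomplete data can lose a whole patient from the HRV comparison for one unusable recording out of eight; a mixed model on all available recordings would not

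*Combined protocol and SAP*

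**What the plan says.** Section E (Statistical methods) gives one method for every continuous outcome: "Continuous variables will be compared between the groups using repeated measures analysis of variance (ANOVA"). It adds follow-up of significant interactions, Tukey adjustment for pairwise tests and a 0.05 threshold. It names no missing-data rule, analysis population or principle of analysing sessions as allocated.

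The design is a 2x2 crossover: "All patients will receive 2 separate, 1-hour sessions, at least 1 day apart, of active and sham LLTS". For Aim 2, "serial 5-minute ECGs will be obtained for HRV analysis every 15 minutes of stimulation (total of 4 recordings") at each visit. For Aim 1 there is one echo per session: "Echocardiography will be performed after 30 minutes of LLTS or sham stimulation to assess diastolic function".

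Under Patient enrollment, "A maximum of 26 patients meeting the inclusion criteria and not meeting the exclusion criteria will be enrolled in the study". No replacement or dropout allowance is given. Section H mentions dropouts only as cases to be looked at one by one in order to improve study conduct, and says nothing about their data.

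**The concern.** Classical within-patient repeated measures ANOVA needs every cell filled. With eight HRV cells per patient, a small failure rate per recording becomes a much larger rate per patient, and the cap of 26 means that lost patients are not made up. One noisy ECG could cost the other seven recordings from that patient. Because the plan is silent, the handling would also be chosen after the data are in, by the investigators who analyse them.

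Timing adds to this. The echo and ECG times are expressed in minutes of stimulation, and no section says what is measured if a session is shortened. The risk section lists effects reported with this type of stimulation, including "painful stimulation, dizziness, mild dyspnea and headaches", so a shortened session is conceivable.

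What is at stake is the precision of the Aim 2 comparison and, less certainly, whether it still covers all randomised patients.

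**Working it through.** **Inputs from the documents.** 26 patients; 2 sessions each; 4 HRV recordings and 1 echo per session; E/e' 15.2 with SD 6.4; 40% reduction; two-sided alpha 0.05. **Assumed:** m, the chance that a recording is unusable (independent across recordings); s, the chance of skipping session 2; rho, the within-patient correlation of E/e'.

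**1. The plan's own figure.** The difference to detect is 0.40 x 15.2 = 6.08, or 6.08/6.4 = 0.95 SD. Read as a crossover with 26 patients, the SD of the within-patient difference is 6.4 x sqrt(2(1 - rho)), with 24 degrees of freedom. Noncentral t power is about 91% at rho = 0, 97.5% at rho = 0.3 and 99.6% at rho = 0.5. The stated power of more than 80% is therefore reproduced on the crossover reading for any rho of zero or more.

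**2. Complete HRV patients.** Recordings per patient: 4 x 2 = 8. P(complete) = (1 - m)^8 when nobody skips session 2.

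| m (assumed) | P(complete) | Complete of 26 | sqrt(26 / complete) | Simulated SE ratio |
|---|---|---|---|---|
| 1% | 0.923 | 24.0 | 1.04 | about 1.04 |
| 2% | 0.851 | 22.1 | 1.08 | about 1.09 |
| 5% | 0.663 | 17.2 | 1.23 | about 1.25 |
| 10% | 0.430 | 11.2 | 1.52 | about 1.55 |

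The last column is the standard error of the active-sham HRV difference from complete patients, divided by the standard error from all available recordings. It was simulated with 26 patients, between-day and within-session SD both 0.5, random gaps and no skipped sessions. A repeat with 40,000 replicates, taking session means of whatever was recorded as the all-available analysis, gave 1.04, 1.09, 1.23 and 1.55. The fourth column is a rough check: if the all-available analysis keeps nearly all the information, the ratio should be close to sqrt(26 / complete), and it is.

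Squaring the ratios gives the equivalent inflation in patients: 1.04^2 = 1.08, 1.09^2 = 1.19, 1.25^2 = 1.56, 1.55^2 = 2.40.

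**3. Skipping session 2.** With s = 8% and no other gaps, the ratio is 1.00. A patient with one session has no within-patient contrast, so both analyses lose the same information.

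**4. Shortened sessions.** With 5% of sessions stopped early (assumed) and no other gaps, the ratio is about 1.05.

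**5. Echo.** Only two measurements are needed: 26 x (1 - m)^2 x (1 - s). At m = 2%, s = 0 this is 25.0; at m = 5%, s = 10% it is 21.1. On the crossover reading, E/e' power stays at or above 80% down to 20 patients at rho = 0, 15 at rho = 0.3 and 11 at rho = 0.5.

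**6. HRV power.** No HRV effect size or SD is given, so a loss of HRV power cannot be computed. Only relative precision can.

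**The case against.** The strongest reply is that the plan never says complete-case. That is correct. A reader might infer that patients will certainly be dropped, but the documents show only that handling is unspecified and that the classical form of the named method drops them. If sessions rather than patients were the unit, a gap would remove a session. Recordings would still be lost, and the crossover pairing would be ignored.

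The size depends on an assumed rate. These are resting 5-minute ECGs, and at 1% to 2% unusable the ratio is only 1.04 to 1.09. This stands, so the result must be read as a range that starts near 1.

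The timing wording ("Echocardiography will be performed after 30 minutes of LLTS or sham stimulation" and "every 15 minutes of stimulation (total of 4 recordings")) can be read as ordinary elapsed time in a one-hour session. A reader might infer that measurements are cancelled when stimulation stops, but nothing says so. The exact ECG times are not given either. If they were 0, 15, 30 and 45 minutes, stopping after the last would lose nothing. The protocol also describes the side effects as minor and sets amplitude at sensory threshold, so early stopping may be rare. What remains is an ambiguity worth one sentence.

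Two further inferences are tempting. One is that the trial's stated power is lost. It is not: the sample size rests on E/e', which has room for loss on the crossover reading. The other is that unequal tolerance of tragus and ear lobe turns the randomised comparison into a biased comparison of completers. That is possible, but the documents give no tolerance data by site, and the simulation used gaps unrelated to treatment, so it measures precision only.

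**Conclusion.** The concern holds in a limited form. For an outcome with eight recordings per patient, the plan names a method whose classical form discards a patient for one gap, and it gives no rule to prevent this. The loss falls on HRV (Aim 2). The standard error is inflated by about 4% at an assumed 1% of unusable recordings, 9% at 2%, 25% at 5% and 55% at 10%. These figures assume independent gaps, equal between-day and within-session SD, and patient-level deletion.

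The direction does not depend on the rate; the size does. The echo comparison is little affected, and neither lost E/e' power nor treatment-related bias is established. The change is still worth making, because the better method is cheap and should be fixed before the data are seen.

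**What to change.** **Section E.** Replace repeated measures ANOVA with a likelihood-based linear mixed model. Fixed effects: treatment, period, sequence, time and treatment-by-time. Random effects: patient and patient-by-session. Use every available recording and analyse sessions as allocated. For the echo outcomes, with one value per session, the time terms and the patient-by-session effect drop out.

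**Section D, Specific Aims 1 and 2.** State that echo and ECG times are counted by the clock from the start of the session. State that recordings are taken as scheduled, where the patient agrees, even if stimulation was shortened, and that the minutes delivered are recorded.

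No change is proposed to when stimulation is stopped or whether a further session is given.

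**Cost.** These are wording changes in two sections, with no added patients and one added data item. The model assumes that data are missing at random, which cannot be verified. Counting shortened sessions as allocated may dilute the estimated effect. The model recovers little from patients who have only one session.
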